**A Phase I/II Randomized, Double-Blinded Standard of Care (Corticosteroid vs Sterile Amniotic Fluid for Osteoarthritis**

**PI: [name].**

**Version: 5.00 dated 23MAY2023**

**SYNOPSIS**

Title	A Phase I/II Randomized Double-Blinded Standard of Care (Corticosteroid) vs. Sterile Amniotic Fluid for Osteoarthritis
Short Title	pAF for the treatment of Osteoarthritis
IRB Number	128491
IND	IND # 26443
Phase	Phase I/II
Design	This is a Phase I/II Randomized Double-Blinded Standard of Care (Corticosteroid) vs. Sterile Amniotic Fluid for Osteoarthritis
Study Duration	3 years
Study Center(s)	University of Utah Orthopedic Center
Objectives	
Primary Objectives:
 

• To determine the safety of using processed Amniotic Fluid (pAF) in patients with osteoarthritis

• To determine the need for repeat intra-articular injection

 
Secondary Objectives:
 

• To determine the pain level following the injection of AF relative to corticosteroids

• To evaluate functional outcomes

Number of Subjects	60 patients

**A Phase I/II Randomized, Double-Blinded Standard of Care (Corticosteroid vs Sterile Amniotic Fluid for Osteoarthritis**

**PI: [name].**

**Version: 5.00 dated 23MAY2023**

Diagnosis and Main Eligibility Criteria	
Inclusion:
 

1. Patients who are between the ages of 18-75 years; and

2. A confirmed diagnosis of knee osteoarthritis based on clinical and radiographic findings consistent with Kellgren-Lawrence Stage 2-3 disease; and

3. Patients who have failed conservative treatment (e.g. steroid, activity modification, therapy, etc.) within 3 months; and

4. Unilateral or bilateral chronic knee joint pain >4 months; and

5. Patients who are able to ambulate (i.e. not wheelchair bound); and

6. Patient reported a typical pain of at least 4 out of 10 during the past week using VAS numeric pain scale (0-10)

 
Exclusion:
 

1. Subjects who have had a previous injection (i.e. steroid, platelet rich plasma, or other) within the last 3 months; or

2. BMI >40 as defined by NIH Clinical Guidelines Body Mass Index; or

3. Concurrent participation in another investigational trial involving systemic administration of agents (within the previous 30 days) or plans to participate in any other allogeneic stem cell therapy trial during the 12 month follow-up period; or

4. Clinical suspicion of infection at injection site; or

5. Any surgeries within 4 weeks, other than diagnostic surgery; or

6. Insulin or self-reported non-insulin dependent diabetic evident of HgA1c <math>\geq 8\%</math> among known diabetics; or

7. Unable to consent to an English Language Consent Form; or

8. Frank mechanical issues (i.e. locking of the knee); or

9. Workman's Compensation cases; or

---	--

**A Phase I/II Randomized, Double-Blinded Standard of Care (Corticosteroid vs Sterile Amniotic Fluid for Osteoarthritis**

**PI: [name].**

**Version: 5.00 dated 23MAY2023**

	

10. Rheumatoid arthritis; or

11. Patients with a known allergy to local anesthetics or components of the study drug (pAF or steroid injection); or

12. Patients with vascular claudication or neurologic disorders affecting the index lower limb; or

13. Patients with inflammatory arthropathies or connective tissue disorders; or

14. Patients with known alcohol or drug abuse or dependence, recreational use of illicit drug or prescription medications, or have used medical marijuana within 7 days of study enrollment; or

15. Patients with history of active cancer/malignancy within 2 years of screening, apart from adequately treated basal cell or squamous cell carcinoma of the skin not associated with the target knee; or

16. Women who are nursing or pregnant; or

17. Patients of childbearing potential who are unwilling to use adequate contraception for 90 days after study drug injection.

Study Product, Dose, Route, Regimen	Standard of care steroid injection includes corticosteroids (40mg/cc Kenolog, 2ml of Ropivacane [3mL total]). The amniotic fluid injection will also be given as 3mL of drug injected directly into the knee.
Statistical Methodology	The primary endpoint (i.e. need for a repeat injection) will be compared between the two arms using Fisher's Exact test. An alpha 0.05 will be used as the threshold for statistical significance.

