**Screening and Enrollment**

Patients will be screened and consented at the University of Utah Orthopedic Center and all participating sub-investigator's clinics when they come for a standard of care physical exam. During this exam, the patient will be asked about their health and lifestyle, medical history, and current medications. As part of the SOC physical exam, the patient will also have standard of care pre-treatment x-rays, neurological assessment, and a diagnosis of mild to severe OA in the knee joint assessment. The patient will also complete standard of care questionnaires including pain assessment and outcome surveys which are described below:

- Pain will be measured by the Visual Analog Scale for pain (VAS Pain). VAS Pain is a patient-reported measurement tool used to quantify perceived level of pain, graded on a scale from 0 to 10 with 0 representing no pain and 10 representing the worse pain possible, and with precise measurement of the marked pain level's distance from 0 comprising the pain level.
- Functional outcomes will be assessed using Single Assessment Numerical Evaluation (SANE), PROMIS Physical Function CAT (PF CAT), and Knee Injury and Osteoarthritis Outcome Score (KOOS) scoring scales.
  - The SANE asks the patient to evaluate their percentage of normal on the affected joint or region of interest. This is a one-question survey with a scale from 0-100%.
  - The PFCAT is a bank of 160 questions related to physical function. It is a computerized adaptive test that asks the patient to self-report capabilities rather than actual performance of physical activities. It includes functioning of upper extremities, lower extremities, and central regions. It also assesses instrumental activities of daily living, such as running errands.

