**Randomization**

Consented patients will be randomized into two groups at a 1:1 ratio using block permutations of 2 and 4. Randomization will be done using either an online randomization service or envelope system. Randomization will occur following the patient's consent into the study, either at the initial visit or the day of the planned injection. Once the randomization number is obtained, unblinded research staff will prepare the appropriate study drug. The injections will be blinded to the research coordinator in charge of data entry, the treating physician and the patient. Clinical staff will prepare the study drug injection and maintain the blind by placing a blank label over the syringe to ensure that the treatment is blinded to the patient and treating physician. Once a patient has been randomized, they become an enrolled subject and will be included in the intention to treat analysis of the trial outcomes, regardless of whether or not they receive study drug.

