**DATA ANALYSIS**

The primary endpoint (need for a repeat injection) will be compared between the two arms using Fisher's Exact test. An alpha 0.05 will be used as the threshold for statistical significance. Missing data will remain missing rather than be imputed since this is a pilot study assessing preliminary safety and feasibility.

The secondary endpoint (pain) will consist of a comparison of mean values for VAS scoring scales pre-injection and at follow-up visits at 1, 3, 6 and 12-months. Clinically significant outcomes will be determined based on the minimal clinically important difference (MCID) occurring for each respective scale, which is defined as the smallest change score needed for the effect to be considered clinically relevant.

Continuous secondary and exploratory endpoints will be compared between arms using Wilcoxon Rank Sum tests. Categorical endpoints (including safety outcomes) will be compared between arms using Chi-squared tests. In cases of small counts, exact tests may be used.

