**SAMPLE SIZE CALCULATIONS AND STATISTICAL POWER**

The primary endpoint is the need for a repeat injection. Based on historic data, about 50% of individuals who receive a steroid injection return for an additional injection within six months due to pain. Assuming a significance level of 0.05 and a need for a repeat injection in the AF arm of 10%, with 60 total patients (30 per arm), we have about 90% power to detect a difference in need for repeat injections at 6 months between the two arms. Expecting approximately 5 randomizations per week, 60 patients will take approximately 3 months to enroll.

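### The primary Fisher test makes no use of baseline pain: it is valid and its stated power is right, but a prespecified adjustment for baseline VAS would gain power and robustness at no patient cost

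*Combined protocol and SAP*

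**What the plan says.** The Synopsis (Statistical Methodology) says: "The primary endpoint (i.e. need for a repeat injection) will be compared between the two arms using Fisher's Exact test". The Data Analysis section repeats this: "The primary endpoint (need for a repeat injection) will be compared between the two arms using Fisher's Exact test", and adds "An alpha 0.05 will be used as the threshold for statistical significance". It names no covariate, effect estimate or confidence interval for this endpoint. The only sensitivity analysis, under Primary Endpoint, counts rescue injections over a year.

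On allocation, the Randomization section says: "Consented patients will be randomized into two groups at a 1:1 ratio using block permutations of 2 and 4". No stratification factor is given.

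On baseline data, Screening and Enrollment says: "The patient will also complete standard of care questionnaires including pain assessment and outcome surveys which are described below". The list includes VAS pain, the study calendar schedules a pain assessment at screening/baseline, and entry requires a typical pain of at least 4 out of 10.

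Two places link the endpoint to pain. Under Primary Endpoint, rescue may be required or requested and is given at the investigator's discretion. The sample-size section says that "about 50% of individuals who receive a steroid injection return for an additional injection within six months due to pain".

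**The concern.** If patients with more pain at entry are likelier to come back for an injection, a chance difference in baseline pain between arms of 30 passes straight into the crude comparison of proportions. Fisher's test has no means of correcting it, and the randomisation does nothing to prevent it. If the arms turn out visibly unequal, the plan offers no prespecified adjusted result, and any adjustment chosen afterwards will be open to challenge. The trial would also have collected, for every patient, a likely predictor of the primary event and left it out of the primary analysis.

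**Working it through.** **Inputs from the plan.** 30 per arm; repeat-injection rates of 50% (steroid) and 10% (pAF); alpha 0.05 (sidedness not stated, two-sided taken); blocks of 2 and 4.

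**Assumption.** The odds ratio (OR) for rescue per SD of baseline VAS is 2, range 1.5–3. The documents give no value.

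**1. The plan's own figure.** The plan says "with 60 total patients (30 per arm), we have about 90% power to detect a difference". Exact power is the sum over all (i, j) of Bin(i; 30, 0.5) × Bin(j; 30, 0.1), counting pairs where Fisher's two-sided P ≤ 0.05. The result is 91.4%, so the stated figure reproduces.

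**2. Actual size of Fisher's test.** The same sum with equal rates gives 2.6% at a common rate of 30% and 2.7% at 50%. The test is valid and conservative.

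**3. Chance imbalance.** The SE of the difference in mean baseline VAS is √(2/30) = 0.258 SD. Then 0.5/0.258 = 1.94, so the probability of a difference above 0.5 SD is 5.3%, split equally between the two directions.

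**4. What 0.5 SD does to the risk difference.** Let p(x) = expit(a + x·ln OR), with x standard normal and a set to give the overall rate. The shift under no treatment effect is E[p(x + 0.25)] − E[p(x − 0.25)]:

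| OR per SD | overall rate 50% | overall rate 30% |
|---|---|---|
| 1.5 | 4.9 points | 4.1 points |
| 2 | 7.8 points | 6.6 points |
| 3 | 11.0 points | 9.4 points |

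For scale, the SE of the risk difference at 50% per arm is √(2 × 0.25/30) = 12.9 points, so 7.8 points is 0.6 SE.

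**5. Power given an unlucky or lucky draw.** Simulation at 50% v 10%, OR 2, imbalance of at least 0.5 SD: Fisher power is 77% when pAF has the worse baseline and 98% when it has the better one. A logistic model adjusted for the covariate has about 95% both ways.

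**6. Power averaged over all draws.** Simulation at OR 2. The adjusted test re-randomises within blocks of 2 and 4, using residuals from a logistic model fitted without the arm. A pure-noise covariate shows what the change of test alone achieves.

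| Rates | Fisher | Re-randomisation, noise covariate | Re-randomisation, baseline VAS |
|---|---|---|---|
| 50% v 10% | 92.0% | 93.9% | 95.9% |
| 50% v 20% | 60.0% | 67.8% | 72.7% |

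Type I error of the adjusted test was 5.0–5.2%. The gain splits as follows:
- 50% v 10%: 93.9 − 92.0 = 1.9 points from the finer test distribution, and 95.9 − 93.9 = 2.0 from VAS.
- 50% v 20%: 67.8 − 60.0 = 7.8 points from the finer distribution, and 72.7 − 67.8 = 4.9 from VAS.

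**7. A second method.** Power of the adjusted logistic likelihood-ratio test minus that of an unadjusted Pearson test, for OR 1.5, 2 and 3: about 1, 1.5 and 3 points at 50% v 10%, and about 3, 5 and 10 points at 50% v 20%. Its type I error was about 5.0–5.7%, slightly liberal. Across methods, the part due to VAS is about 1–4 points at 50% v 10% and 1–10 points at 50% v 20%.

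**The case against.** The strongest reply is that nothing here is broken. Randomisation protects Fisher's test, chance imbalance is not bias on average, and the 91.4% already averages over lucky and unlucky draws. That stands in full. A reader might infer from step 5 that the stated 90% is wrong, but the loss on one side is matched by a gain on the other.

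The second reply is that most of the visible gain is not baseline information. That also stands in part. At OR 2, about half the gain at 50% v 10% (1.9 of 3.9 points) and about 60% at 50% v 20% (7.8 of 12.7) comes from leaving a conservative discrete test.

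Third, the strength of the link between baseline VAS and rescue is assumed. The entry rule of at least 4 out of 10 narrows the range of VAS, and rescue also depends on later pain and on judgement. This is fair. At OR 1.5 the covariate is worth only about 1 point at the planned effect.

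Fourth, the Data Analysis section calls this a pilot, and only 15 + 3 = 18 events are expected. That argues for one covariate and a method that tolerates sparse events. It does not argue against adjustment, because the plan sets a formal alpha and power, and chance imbalance is largest in small trials.

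Finally, it is tempting to add Kellgren-Lawrence grade as a second covariate that is already in hand. The documents do not support this. They require findings consistent with stage 2–3, but neither the study calendar nor the Data Collection section lists the individual grade as a recorded variable.

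**Conclusion.** The point holds as a worthwhile improvement, not as a fault. The planned test is valid and its power statement is correct; the documents do not support reading the unadjusted analysis as biased or the trial as underpowered for its stated effect.

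What is lost is a modest amount of power at the planned effect, a larger amount if pAF does less well than hoped, and protection against a baseline imbalance above 0.5 SD, which about 1 trial in 20 of this size will show. The case rests on baseline VAS predicting rescue with an OR of about 1.5–3 per SD. The plan's wording makes a link plausible but does not quantify it. If there were no link, adjustment would cost little: the noise-covariate results in step 6 are still no worse than Fisher's.

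**What to change.** In the Synopsis (Statistical Methodology) and in Data Analysis, prespecify a primary analysis adjusted for baseline VAS alone:

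- **Test:** a re-randomisation test that follows the blocks of 2 and 4, on residuals from a logistic model of 6-month rescue on baseline VAS fitted without the arm term. Leaving the arm out avoids separation if pAF has very few events.
- **Estimate:** the risk difference standardised over baseline VAS, with a 95% CI.
- **Support:** Fisher's exact test as the unadjusted analysis.

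If the sponsor prefers to keep Fisher's test for the P value, the VAS-standardised risk difference with its 95% CI should still be the prespecified effect estimate. Add Kellgren-Lawrence grade only if the individual grade is recorded.

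The cost is some analysis-plan wording and a short program. It needs no extra patients, visits or data. The change should be made before unblinding.

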**STUDY SUMMARY**

This study will look at blinded standard of care (SOC) steroid injection vs. amniotic fluid injection (pAF) to treat and reduce osteoarthritis (OA) inflammation and pain. The main objectives of this study are to establish the safety and tolerability of allogeneic intra-articular pAF injections. Secondary objectives include pain levels and functional outcome scoring in patients over a 12 month time frame.

**OUTCOMES OF THE STUDY**

### **Primary Endpoint**

- The need for a repeat allogeneic intra-articular injection [Time Frame: 6 months].

Participants in both the SOC and pAF treatment arms may require and/or request rescue medication (i.e. SOC injection) at any time and will be given per PI discretion as part of standard of care. The clinicians will not know which study arm the study participant is in but will treat the participant with the SOC injection. This information will be documented and collected in the Electronic Medical Record (EMR), as well as the study's electronic data capture system. Participants will not be given any additional pAF injections throughout the 12-month study period.

The participant will continue to be treated with SOC injections as needed. The outcome will be an indicator of whether or not a subject received a rescue medication within 6 months. Sensitivity analyses will also be performed to assess the number of rescue medications given over the course of a year.

### **Secondary Endpoints**

- Pain level following the injection based on Visual Analog Scale scoring. [Time Frame: 6 months]

Pain will be measured by the Visual Analog Scale for pain (VAS Pain). This will consist of a comparison of mean values for VAS scoring scales pre-injection and at the 6 month follow-up assessment. Clinically significant outcomes will be determined based on the minimal clinically important difference (MCID) occurring for each respective scale, which is defined as the smallest change score needed for the effect to be considered clinically relevant; described below. Specifically, VAS represents a patient-reported measurement tool used to quantify perceived level of pain, graded on a scale from 0 to 10 with 0 representing no pain and 10 representing the worse pain possible, and with precise measurement of the marked pain level's distance from 0 comprising the pain level.

- Functional outcomes scoring using Single Assessment Numerical Evaluation (SANE), PROMIS Physical Function CAT (PF CAT), and Knee Injury and Osteoarthritis Outcome Score (KOOS) scoring scales. [Time Frame: 6 months]

Functional outcomes will be evaluated throughout the study period. The SANE asks the patient to evaluate their percentage of normal on the affected joint or region of interest. This is a one-question survey with a scale from 0-100%. The PFCAT is a bank of questions related to physical function. It is a computerized adaptive test that asks the patient to self-report capabilities rather than actual performance of physical activities. It includes functioning of upper extremities, lower extremities, and central regions and also assess instrumental activities of daily living, such as running errands. The KOOS is a survey that assesses joint symptoms, pain, pain during daily activities, physical function in daily living, as well as physical function during sports or

**A Phase I/II Randomized, Double-Blinded Standard of Care (Corticosteroid vs Sterile Amniotic Fluid for Osteoarthritis**

**PI: [name].**

**Version: 5.00 dated 23MAY2023**

recreational activities. It also assesses quality of life. These functional outcome scores will be assessed at time points: 1, 3, 6 and 12 months.

**Exploratory Endpoints**

- Number of treatment emergent adverse events (AEs) directly related to the injection. [Time Frame: 1 day, 2 days, 1 month, 3 months, 6 months and 12 months]
- Pain level following the injection based on Visual Analog Scale scoring. [Time Frames: 1, 3, 6 and 12 months]
- Functional outcomes scoring using Single Assessment Numerical Evaluation (SANE), PROMIS Physical Function CAT (PF CAT), and Knee Injury and Osteoarthritis Outcome Score (KOOS) scoring scales. [Time Frames: 1, 3, 6 and 12 months]

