**Time Period for Adverse Events**

For purposes of this study, events that occur following randomization through the last follow-up visit at 12 months will be reported as adverse events. Serious adverse events, unexpected medically attended events, and new onset chronic illnesses will be recorded from randomization through twelve months after the last study dose. Specifically, events that occur following informed consent to participate in the study, but prior to actual randomization, are not adverse events. These should be recorded as baseline conditions.

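### Adverse events are compared by arm to month 12 with no split at rescue, and the endpoint does not say whether reactions to rescue injections count

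*Combined protocol and SAP*

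**What the plan says.** The Synopsis of the combined protocol and SAP lists the safety of pAF as a primary objective. The matching endpoint stands under Exploratory Endpoints: "Number of treatment emergent adverse events (AEs) directly related to the injection", at 1 and 2 days and at 1, 3, 6 and 12 months. Under Time Period for Adverse Events, "events that occur following randomization through the last follow-up visit at 12 months will be reported as adverse events". Under Data Analysis, "Categorical endpoints (including safety outcomes) will be compared between arms using Chi-squared tests", with exact tests allowed for small counts.

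Under Primary Endpoint, participants in both arms may receive rescue at any time. Rescue is always the SOC injection, pAF is never repeated, and "The participant will continue to be treated with SOC injections as needed". The sample size section expects that "about 50% of individuals who receive a steroid injection return for an additional injection within six months due to pain", and assumes 10% in the pAF arm.

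The relatedness definitions tie causality to the assigned study intervention. An event clearly due to another therapeutic intervention is Not Related. One that fits the timing but could have had another cause is Possibly Related. The expected events are injection-site pain, swelling or effusion, soreness and bleeding.

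No section ends the adverse event window at rescue, separates events before and after it, or adjusts for the number of injections. The only sensitivity analysis on rescue concerns the number of rescue treatments given.

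**The concern.** A rescue injection is a further injection into a knee, and any such injection could produce the expected events listed in the plan. If the efficacy hypothesis is right, SOC participants receive more of these injections than pAF participants. A by-arm count that includes events after rescue then mixes the reaction risk of each product with the number of injections given. In the pAF arm, events after rescue also reflect exposure to both pAF and steroid.

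What is at stake is the reading of a primary objective. The endpoint leaves *the injection* undefined, and *directly related* matches none of the three relatedness categories. The same data could therefore give two different safety tables, depending on a choice made after the events are known.

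**Working it through.** **Inputs from the plan.** 30 participants per arm; repeat injection by month 6 in 50% (SOC) and 10% (pAF); alpha 0.05; Fisher's exact test for the primary endpoint. Sidedness is not stated; two-sided is assumed.

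**The plan's own figure.** Exact power is the sum, over all pairs of outcomes (i, j) with a Fisher p-value of at most 0.05, of Bin(i; 30, 0.50) × Bin(j; 30, 0.10). The result is 91.4%, which agrees with the stated 90% or so. The 50% and 10% rates are thus the ones the design rests on.

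**Injections by month 6, at most one rescue each.**
- Participants rescued: 30 × 0.5 = 15 (SOC) and 30 × 0.1 = 3 (pAF).
- Total injections: 30 × 1.5 = 45 and 30 × 1.1 = 33; ratio 45/33 = 1.36.

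**Expected events if post-rescue events count.** The documents give no reaction risk per injection. Assume the same risk r for both products, with every reaction detected and counted. Expected events are 45r and 33r:

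| r | SOC | pAF |
|---|---|---|
| 5% | 2.25 | 1.65 |
| 10% | 4.5 | 3.3 |
| 20% | 9.0 | 6.6 |
| 30% | 13.5 | 9.9 |

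Participants with at least one event, at r = 20%: 1 − 0.8 × (1 − 0.5 × 0.2) = 28.0% (SOC) and 1 − 0.8 × (1 − 0.1 × 0.2) = 21.6% (pAF). At r = 10% the figures are 14.5% and 10.9%. There is no true difference in any of these cases.

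**Masking.** Let q be the reaction risk of the pAF study injection. Expected counts are equal when 30(q + 0.1r) = 30 × 1.5r, so q = 1.4r for any r. For participants with an event, the break-even is slightly lower: at r = 20%, 1 − q = 0.72/0.98, so q = 26.5%, or 1.33 times r.

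**Effect on the test.** With equal true risk, the chance of a significant chi-squared result rises from 4.9% to 8.6% at r = 20%, and from 5.4% to 7.5% at r = 10%. The harm lies mainly in the descriptive comparison.

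**Month 12.** The plan gives no rates beyond month 6. If the 6-month rates persist (an assumption), total injections are 52.5 and 35.7 counting first rescues only (ratio 1.47), 60 and 36 with one chance of rescue per six months (1.67), and about 72 and 36 at a constant repeat rate (1.97).

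**With the split.** Each participant has one study injection before rescue, so exposure is 30 and 30. At r = 10%, 3.0 and 3.0 acute reactions are expected.

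**Why not person-time for acute reactions.** Assume constant rescue hazards that give 50% and 10% at month 6: h = ln 2/6 = 0.1155 and −ln 0.9/6 = 0.01756 per month. Mean time to first rescue or month 12 is (1 − e^(−12h))/h: 0.75/0.1155 = 6.5 months (SOC) and 0.19/0.01756 = 10.8 months (pAF). At r = 20%, each arm has 6 reactions to the study injection, yet the SOC rate is 10.8/6.5 = 1.67 times the pAF rate. That artefact is larger than the 36% above and also favours pAF.

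**The case against.** The strongest reply is that the plan already limits the endpoint. It counts only injection-related events, and elsewhere the same phrase means the study injection, while rescue has its own names. Relatedness is anchored to the assigned intervention, so a clear reaction to a rescue can be classed as Not Related. If every post-rescue event is classed that way, the excess is zero. This stands for clear cases. Not Related, however, requires that another cause be clear, and ambiguous events stay in as Possibly Related. The Data Analysis sentence on safety outcomes is also not confined to related events.

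Second, the 24- and 48-hour calls fall almost entirely before any rescue, and that is when injection-site reactions are expected. An acute excess with pAF should show there. This stands, and the proposed summary should lead with those time points. No such calls are scheduled after a rescue, so rescue reactions may be under-detected, and the 36% assumes that they are not.

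Third, comparing randomised arms over 12 months is a valid comparison of treatment strategies. That stands too; the table misleads only if read as the safety of the pAF injection itself.

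A reader might infer that in the SOC arm relatedness cannot tell study from rescue reactions because the product is the same. The documents do not support this for acute events: the treating physician is blinded, and onset and repeat-injection dates are recorded. Only ambiguous, later events remain. Nor does safety rest on this comparison alone: the plan has staggered entry for the first six participants, stopping criteria, and an unblinded DSMB that reviews all adverse events.

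**Conclusion.** The point holds in conditional form. The plan compares adverse events by arm to month 12, does not define which injection the endpoint refers to, and has no split at rescue. If post-rescue events are counted, the planning rates give 36% more injections in the SOC arm by month 6, and a pAF reaction risk up to about 1.4 times that of steroid could be masked. The 36% rests on one rescue per rescued participant. The events it implies further assume equal risk per injection and full detection and counting of rescue reactions.

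A reader might infer that pAF will look safer than it is. The documents do not establish this. The direction depends on the 50% and 10% rates: equal rescue removes the distortion, and more rescue in the pAF arm reverses it, because steroid reactions would then be charged to pAF. Five to one describes participants rescued (15 and 3), not total injections. This is a cheap improvement that should be made because safety is a primary objective; it does not invalidate the trial.

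**What to change.** - Under Exploratory Endpoints, define *the injection* as the study injection, and state which relatedness categories count as directly related.
- Keep the 12-month by-arm table, labelled as the comparison of treatment strategies.
- Add a between-arm summary of participants with an adverse event whose onset falls after the study injection and before first rescue, led by the existing day 1, day 2 and 1-month time points.
- List events after first rescue separately by arm.
- Do not use person-time rates for acute injection reactions. If they are used at all, keep them for late-onset events and note that the cut at rescue depends on outcome.

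The cost is a few sentences in the analysis section and one derived before/after-rescue variable. Repeat-injection dates (Data Collection) and adverse event onset dates (Adverse Event Reporting) are already collected, so no new visits or participants are needed. The downside is a little more analysis, and a pre-rescue summary with shorter follow-up in whichever arm has more rescue.
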